### 6.2 Study Procedures:

Following successful screening (see below), participants will review an online consent form which overview the study, study tasks, outlines risks and benefits, strategies to reduce risks, and risk-benefit analysis. After this, they participate in an initial telephone call from the project coordinator where they have the opportunity to ask any questions and have them answered, as well as verify information for cross-validation purposes. Then, if confirmed eligible and unique, they receive access to the baseline survey. Participants who complete the baseline survey will then be randomized, via a computer assignment, to a treatment or control group.

Participants in the control group will be notified by email. Thereafter, they will be contacted occasionally with survey links and reminders. As needed, additional casual communications will be used to increase retention.

Participants in the treatment group will be emailed immediately with a username and password to access the intervention. They will be mailed their welcome packet within one week.

Surveys will be conducted at baseline, and at 3, 6, 9, 12, 18, and 24 months follow-up. Surveys are attached.

Interaction for all participants in our study will include an online screening survey, a vetting phone conversation, an email confirmation, followed by an online baseline survey and five follow-up surveys. In addition, all participants can contact the study at any time using a 1-800 and/or our study email. In all email and phone contact, we will maintain HIPPA compliant standards to ensure no privacy violations. (e.g., we will not describe the nature of the study in phone or email messages). In addition, data will be maintained in password protected files on a secure server.

### 6.3 Follow-Up:

Participants will be followed for twenty four months. Participants randomized to the intervention group will have access to the website and forums throughout the two years; however, it is anticipated that participants will experience the bulk of the intervention experiences during the first year. Sildenafil will only be provided for the first twelve

**PROTOCOL TITLE: Restore: Gay Men and Prostate Cancer Aim III**

months. All participants will receive follow-up surveys at months 3, 6, 9, 12, 18, and 24 (attached).

**6.4 Individually Identifiable Health Information:**

Attached

**7.0 Data Banking**

N/A

**8.0 Sharing of Results with Participants**

The results of this study will be made available to interested participants through the use of lay summaries posted on our website. Our format is to use executive summaries which report in lay language the main results of the study. In addition, we will email updates, including reports and publications to participants. Participants may choose to opt out of email updates.

**9.0 Study Duration**

**9.1 Describe:**

The duration anticipated for an individual participant's participation in the study. The total duration of participation is 24 months. Follow-up surveys will occur for both treatment and control groups at baseline, 3, 6, 12, 18, and 24 months. For participants in the treatment group, PDE5-I drugs will be provided for 12 months, but the online intervention will continue for 24 months.

The duration anticipated to enroll all study participants. We expect enrollment to last 13 months from January 2019 through February 2020. The duration anticipated to complete all study procedures and data analysis. The study will take five years total, including 15 months of preparation, 37 months of recruitment and intervention, and eight months for analysis.

**10.0 Study Population**

**10.1 Inclusion Criteria:**

Each participant must be:

- An adult biological male who has had sex with a man or men
- Diagnosed with PCa and treated or pending treatment, including but not limited to radical prostatectomy, radiation, and/or hormone therapy
- Recent problems with sexual and/or urinary function
- Living in the United States or its territories
- A unique, validated individual

PROTOCOL TITLE: Restore: Gay Men and Prostate Cancer Aim III

10.2 Exclusion Criteria:

- Cognitive Impairment
- Non-English speaking/reading
- Patients who underwent a bi-lateral, non nerve-sparing, prostatectomy (for which rehabilitation is not recommended as efficacious).

10.3 Screening:

Participants will complete an online screening survey to evaluate inclusion criteria (attached). Upon completion of the screener, study staff will call each participant to confirm identity, confirm screening survey answers and evaluate English and cognitive proficiency. Participants' IP addresses will be used to ensure US location and deduplication.

## 11.0 Vulnerable Populations

11.1 Vulnerable Populations:

- Children
- Pregnant women/Fetuses/Neonates
- Prisoners
- Adults lacking capacity to consent and/or adults with diminished capacity to consent, including, but not limited to, those with acute medical conditions, psychiatric disorders, neurologic disorders, developmental disorders, and behavioral disorders
- Approached for participation in research during a stressful situation such as emergency room setting, childbirth (labor), etc.
- Disadvantaged in the distribution of social goods and services such as income, housing, or healthcare
- Serious health condition for which there are no satisfactory standard treatments
- Fear of negative consequences for not participating in the research (e.g. institutionalization, deportation, disclosure of stigmatizing behavior)
- Any other circumstance/dynamic that could increase vulnerability to coercion or exploitation that might influence consent to research or decision to continue in research
- Undervalued or disenfranchised social group
- Members of the military
- Non-English speakers
- Those unable to read (illiterate)
- Employees of the researcher
- Students of the researcher
- None of the above

11.2 Additional Safeguards:

## PROTOCOL TITLE: Restore: Gay Men and Prostate Cancer Aim III

This study is designed to address health disparities affecting sexual minority men, so inclusion of GBM is central and essential to the study. Stigmatization is the main concern. Multiple stigmas have been identified in this population, however we have taken care to minimize risk of stigma. With these protections, we believe risks will be minimal.

## 12.0 Number of Participants

### 12.1 Number of Participants to be Consented:

We plan to recruit 450 participants: 150 participants who have undergone treatment in the past two years and 300 who have had at least two years since their PCa treatment.

We expect 80% power to detect the statistically significant differences between the intervention group and the control group. The power calculation was based on standardized effect size = 0.35, total number of observations per participant during the course of the study,  $M = 9$ , total number of participants,  $N = 450$ , assumed within-subject variability,  $\sigma^2 = 0.50$ , assumed between-subject variability,  $\tau^2 = 0.20$  and a linear change over time.

## 13.0 Recruitment Methods

### 13.1 Recruitment Process:

Our recruitment strategies, already approved in a separate protocol, will have three arms:

1. **Urology Clinics and other Prostate Cancer Organizations:** In the spring and summer of 2018, we built relationships with prominent urology and oncology clinics, urologists and other prostate cancer specialists working in private practice, and federally-qualified gay health centers and family practice clinics with large gay patient populations, nationwide. These medical sources will provide recruitment materials, such as letters, email invitations or fliers, to their gay and bisexual patients. Additional recruitment partners in this aim may include prostate cancer support groups or community nonprofit organizations aimed at cancer survivors.
2. **Online from Cancer Support Sites:** In our preliminary study, we recruited a sizeable portion of our sample through the online community *Malecare*. We will replicate this successful strategy with both *Malecare* and similar organizations providing online support services to prostate cancer survivors.
3. **Directly from the GBM community:** We will advertise in gay newspapers (eg *Washington Blade*) and in gay men's chorus concerts programs. In addition, we will recruit through organizations designed to serve LGBT seniors, such as SAGE and Prime Timers, and similar organizations which are likely to have large populations of older GBM.

Recruitment procedures are described in detail in approved protocol # STUDY00003361

### 13.2 Source of Participants: *Describe the source of potential participants, e.g., Research Experience Program.*

For most of our recruitment strategies, participants will self-identify in response to flyers or advertisements. In addition, clinicians may contact GBM patients, as identified by

## PROTOCOL TITLE: Restore: Gay Men and Prostate Cancer Aim III

clinics via electronic medical records, in order to recruit them into the study. This process will be carried out entirely by the partnering clinics who currently have access to these records. Partner organizations will be provided with a media packet that includes materials for both passive (e.g. flyers and posters) and active (e.g. letters) recruitment. Recruitment materials will point participants to an online screening survey. Upon completion of the screener, potential participants will be contacted by study staff via telephone. These recruitment materials are attached.

### 13.3 Recruitment Materials:

Our media kit includes:

- Flyers and posters
- Online and print advertisements
- Letters to potential recruiting partners
- Letters to potential participants
- Press release
- Infographics

### 13.4 Payment:

Participants will be paid \$50 after completing the baseline survey, and \$25 for each subsequent survey (3, 6, 12, 18, and 24 months), for a potential total of \$275.

## 14.0 Withdrawal of Participants

### 14.1 Withdrawal Circumstances:

Participants found to be fraudulent or ineligible (i.e. participants utilizing false information to enter the study multiple times) or those who become ineligible (i.e. those who experience cognitive decline during the intervention) may be withdrawn from the study.

### 14.2 Withdrawal Procedures:

Follow-up surveys will be reviewed for suspicious responses. Participants identified as duplicitous will be removed from the study and further follow-up, and their data will not be included in the analysis.

Participants deemed ineligible due to new health concerns or cognition concerns will be removed from the intervention, but will receive follow-up surveys.

Participants identified as ineligible or fraudulent through the course of the intervention (i.e. via information that is shared on a forum) will remain in the study to prevent selection bias, unless there are concerns for their safety.

### 14.3 Termination Procedures:

N/A

## 15.0 Risks to Participants

## PROTOCOL TITLE: Restore: Gay Men and Prostate Cancer Aim III

Foreseeable Risks: We have identified potential risks related to the Aim II study protocol:

1. Risk of breach of confidentiality. Participants are asked to complete the survey in private and to guard their confidentiality, however, the researchers have little control over who else can see the participant. We assess this risk as "unknown."
2. Emotional discomfort with sexual and prostate cancer questions. This survey asks about sexual, bowel and urinary functioning challenges and their impact on sex. These are sensitive areas to be questioned about. While such questions when asked in in-person interviews are potentially embarrassing, it is not clear whether the same questions when asked by computer on a survey are experienced as sensitive. Having had over 15,000 GBM complete sexually focused surveys of similar sensitivity, we note only one man to date reported sensitivity concerns sufficient to contact the study. Our experience suggests such concerns may be rare (and possibly overstated for online surveys).
3. Anxiety and risk of being "outed". Older men, closeted men, and those less comfortable with or more private about their sexuality and/or a diagnosis of prostate cancer may experience anxiety about being "discovered" or "outed" as being gay/bisexual/MSM, living with PCa, or both by some third party, particularly in a recruitment study that involves snowball sampling, public outreach, and communication on sexual functioning. We assess some risk of anxiety as likely.
4. Concern about security of data. Given the potential of any computer system to be hacked, there are concerns in online surveys about security of data. We assess these risks to participants as minimal and have taken steps described below to minimize these risks.

15.1 Reproduction Risks: N/A

15.2 Risks to Others: N/A

## 16.0 Incomplete Disclosure or Deception

16.1 Incomplete Disclosure or Deception:

N/A. We intend to fully disclose and there is no deception.

## 17.0 Potential Benefits to Participants

17.1 Potential Benefits:

Participants in the intervention arm of this study may benefit from the provision of intervention materials worth several hundred dollars. These include free PDE5-I drugs for 12 months, the penile vacuum device, three dildoes (which can double as anal dilators), two penile constriction rings, and access to videos, interactive forums by experts, and the opportunity to read rehabilitation materials tailored to GBM. Participants in the control arm will not receive the direct benefits of the intervention; however, they may benefit from increased assessment or attention from study staff.

17.2 Data Management:

Data will be collected via a series of Qualtrics surveys and managed by study staff.

17.3 Data Analysis Plan:

## PROTOCOL TITLE: Restore: Gay Men and Prostate Cancer Aim III

All analyses will be completed in STATA version 12.0. Comparisons between the intervention and control groups and the outcome measures (EPIC Urinary, Hormone, Sexual, and Bowel, as well as FACT-P and BSI-18 scores) will be evaluated using random coefficient modeling. Stratified analyses will be conducted by time since treatment (2+ years vs <2 years) and relationship status. Models may be adjusted for treatment time, relationship status, comorbidities and demographic variables.

### 17.3 Power Analysis:

We expect 80% power to detect the statistically significant differences between the intervention group and the control group. The power calculation was based on standardized effect size = 0.35, total number of observations per participant during the course of the study, M = 9, total number of participants, N = 450, assumed within-subject variability,  $\sigma^2 = 0.50$ , assumed between-subject variability,  $\tau^2 = 0.20$  and a linear change over time.

### 17.4 Statistical Analysis:

See above

### 17.5 Data Integrity:

In online surveys it is not always possible to restrict the study raising the necessity of having strong de-duplication and cross-validation protocols to detect fraud. Our experience suggests that between 5-99% of online survey responses may be fraudulent necessitating strong protocols to exclude fake and duplicative surveys. In order to guarantee that each survey respondent is a unique, validated individual meeting our eligibility requirements, participants will undergo a two-step screening process, including both an online screening survey and a telephone vetting conversation. Fraud will also be assessed by monitoring recruitment into the study, watching in particular for suspicious entries (e.g., a sudden large participation may signal a bot attack). During de-duplication and cross-validation, participants' entry time on study, duration to complete the survey, IP address, age, and zip codes are monitored, as well as answers to information that only health professionals and patients with prostate cancer are likely to know (e.g. Gleason score; medications). Surveys that are suspicious are initially flagged for closer manual checking. Where a survey is clearly duplicative, only the first complete survey will be deemed unique. Where a survey is clearly invalid, it will be rejected. Only after a survey has cleared the de-duplication and cross-validation protocol will a participant be paid. Finally, in the event of suspicious responses (between valid and clearly invalid), we will email the participant to request clarification of the issue.

## 18.0 Confidentiality

### 18.1 Data Security:

Well-established, state-of-practice, security protocols will be followed. All data will be encrypted, stored on a dedicated server behind a firewall, identifying information will be separated from the data, and all information and data will be accessible only by password to the investigators and their staff. These procedures have proven effective in the prior online studies conducted by this research team.

It will not be appropriate to include a copy of the consent form in participants' medical, employment, or educational records, because we do not have access to those records.

## **19.0 Provisions to Monitor the Data to Ensure the Safety of Participants**

### **19.1 Data Integrity Monitoring.**

Protocols for study procedures, data management, and reporting will be created by the primary investigator in conjunction with study staff. Monitoring of such proceedings will be conducted by the internal methods committee, comprised of the primary investigator, methodologist, and two additional investigators as well as study staff. Reports on data integrity will be presented to this committee quarterly. Reports will include review of data entry and management procedures, recruitment, randomization, participant communication, and surveys. Each report will include notation of adherence to protocols and accuracy of data.

### **19.2 Data Safety Monitoring.**

Data safety will also be monitored and evaluated quarterly by the internal methods committee, as described above. While risks in this study are minimal, adverse events will be recorded as reported. Events related to intervention procedures may include: reactions to PDE5-i drugs, injury related to pelvic floor exercises or pump use, and other adverse events related to the study. Safety data collection will begin as soon as the intervention website is open to participants. Because this study presents minimal risk to participants, we do not anticipate any conditions that will trigger immediate suspension of research.

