## PROTOCOL TITLE: Restore: Gay Men and Prostate Cancer Aim III

- Access to a comprehensive online intervention, including written and video educational materials on each focus area, tracking tools to encourage and measure adherence, supplemental educational materials, and moderated forums.
- Regular contact with study staff, who will encourage adherence, provide advice, and answer questions. In addition, participants will have access to monthly expert webinars, with presentations from specialists in prostate cancer and sexual health.

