### **18.2 Access to Participants:**

Our research team will not have access to medical records. However, in order to evaluate adherence, safety, and analyze the results of our study, we will collect information about PDE5-i use, prostate cancer treatment and side effects, and other health conditions. This information will be stored on password-protected, secured servers and will only be available to research staff who will use it for these purposes.

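### Adverse events are recorded as they are reported while staff contact differs by arm, so reports may be incomplete and unequal; separately, the risk section covers Aim II, not Aim III

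*Protocol*

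**What the plan says.** **Capture of events.** Protocol section 19.2 says that "adverse events will be recorded as reported" and that the internal methods committee reviews safety quarterly. It names the kinds of event it has in mind: "Events related to intervention procedures may include: reactions to PDE5-i drugs, injury related to pelvic floor exercises or pump use", plus other study-related events. On timing it says only: "Safety data collection will begin as soon as the intervention website is open to participants".

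**Contact by arm.** Under section 5.1, intervention men have a coach, moderated forums and "Regular contact with study staff, who will encourage adherence, provide advice, and answer questions". Under section 6.2, control men are told of their assignment by email, and then "they will be contacted occasionally with survey links and reminders", with informal retention messages if needed. Both arms may phone or email the study whenever they wish (sections 6.2 and 20.1), and both receive the same follow-up surveys.

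**Planned health information.** Section 18.2 (Access to Participants) says the team has no access to medical records but, to evaluate adherence, safety and results, "we will collect information about PDE5-i use, prostate cancer treatment and side effects, and other health conditions".

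**Risk section.** Section 1.0 says that this protocol covers Aim III. Section 15.0 opens: "We have identified potential risks related to the Aim II study protocol". It then lists four risks: breach of confidentiality, discomfort with the questions, anxiety about being outed, and data security.

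**Analysis.** Neither the protocol's Data Analysis Plan (section 17.3) nor the SAP contains a safety analysis.

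**The concern.** A rule that records what participants happen to mention depends on how often they have occasion to mention it. Here that opportunity is built in for one arm: staff are regularly in touch with intervention men about the drug, the pump and the exercises. A control man is mostly sent survey links, and an event reaches the study only if he raises it or a survey asks.

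Two things could follow. Events may be missed in either arm, and without medical records the study cannot recover them from another source. The missed share may also differ by arm, so that counts shown to the quarterly review, or quoted in a later statement about the programme's safety, would mix true differences with differences in reporting. Efficacy results are not affected.

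The Aim II wording in section 15 is a separate matter. It concerns which risks were assessed and disclosed, not how events are captured.

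**Working it through.** The plan states no event rate, reporting probability or safety contrast, so there is no figure of its own to reproduce. The check is mainly a comparison of the text.

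**1. Is a solicitation method stated?** Section 19.2 gives no event questions, recall window, grading, seriousness or relatedness definition, or tabulation by arm. It ties the start of collection to the opening of the website, not to randomization. If that means one calendar date it can serve both arms; if it means each man's own access, it is undefined for control men.

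**2. Does section 18.2 supply the method?** In part. It plans collection with safety as a stated purpose, and it lists use of the study drug class and other health conditions. But its mention of side effects follows directly on prostate cancer treatment and can be read as side effects of that treatment. It gives no instrument, timing or arm, and does not mention pump or exercise injuries. The surveys are described as attached but were not available for review. Systematic capture is therefore neither shown nor excluded.

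**3. Does opportunity to report differ by arm?** Yes for contact initiated by staff (section 5.1 against section 6.2). No for contact initiated by the participant or for the scheduled surveys, which are common to both arms.

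**4. What could a reporting gap do?** This is an illustration only. Inputs from the documents: 450 men (section 12.1) randomized 1:1 (section 6.1), so 450 / 2 = 225 per arm. Assumed inputs: a true event rate *p* equal in both arms, and reporting probabilities *c*I (intervention) and *c*C (control).

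- Expected recorded events in an arm = 225 × *p* × *c*
- Recorded risk ratio = (*p* × *c*I) / (*p* × *c*C) = *c*I / *c*C, whatever *p* is

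With *p* = 10%, so that 22.5 true events are expected per arm:

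| Reporting, intervention vs control | Expected recorded events | Recorded risk ratio |
|---|---|---|
| 90% vs 90% | 20.25 vs 20.25 | 1.00 |
| 90% vs 70% | 20.25 vs 15.75 | 1.29 |
| 70% vs 50% | 15.75 vs 11.25 | 1.40 |
| 90% vs 50% | 20.25 vs 11.25 | 1.80 |

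The equal-rate assumption suits only general events that either arm can have, such as unplanned medical care. It does not suit injuries from a device that the study gives to one arm. For those, the issue is completeness: at 50% reporting, half are missed.

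**5. Does section 15 match section 19.2?** No. None of its four risks concerns the drug, the pump or the exercises, all of which section 19.2 names as sources of events, and it attributes its list to another aim. This needs no assumption. Section 22.1 provides consent screens on the study drug and on participant risks; their content was not available, so whether they share the omission is unknown.

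**The case against.** The strongest reply is that recording events as reported does not exclude reports given in answer to survey questions. Section 18.2 plans to collect health information with safety as a purpose, both arms receive the same surveys, and every man can contact the study at any time. This stands as far as it goes: a reader might infer that events are captured only when men volunteer them, and the documents do not support that. Nor do they show the contrary, because section 18.2 is ambiguous and the surveys could not be checked.

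A second reply is that no between-arm safety comparison is planned, so there is no estimate to bias. This also stands. A reader might infer that the safety data are bound to be incomplete, or that harm will be overstated relative to control. Both go too far. The reporting gap is not quantified, its direction is plausible but not established, and the events section 19.2 names are largely specific to the intervention, so equal true rates are not the natural case for them. What remains is the effect on the quarterly review and on any later descriptive statement by arm.

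Third, pump or exercise items would mostly not apply to usual-care men, and men who know their assignment may answer even identical questions differently. Both are fair, and they limit what the fix can achieve.

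Finally, the Aim II wording does not make event data unequal by arm. Agreed; it is kept as a separate point.

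**Conclusion.** The concern holds in limited form. As written, section 19.2 relies on events being reported, while regular staff contact, a coach and forums belong to one arm. Spontaneous reports may therefore be incomplete and may be captured unequally. The size is unknown. Under the assumed reporting probabilities above and equal true rates, the recorded risk ratio ranges from 1.00 (no gap) to 1.80 (90% against 50%). Those inputs are not from the documents, and no significance claim should be built on them.

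If the attached surveys already ask both arms the same event questions, the fault reduces to section 19.2 not saying so.

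The mismatch between section 15 and sections 1.0 and 19.2 is firm and rests on the text alone. Together these are cheap improvements to safety reporting and risk disclosure, not threats to the efficacy conclusions.

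**What to change.** - **Reconcile sections 19.2 and 18.2.** State that the same short event items are put to both arms at each scheduled follow-up survey, and add them if the surveys lack them. Sections 6.2 and 6.3 include a month-9 survey that sections 9.1 and 13.4 omit, so settle the schedule at the same time.
- **Separate the summaries.** Base any by-arm summary on general items that apply to everyone, for example any drug reaction, any injury, and any unplanned medical care. List device- and exercise-specific items, and spontaneous reports, separately.
- **Correct section 15 as its own edit.** Reconcile it with Aim III and with the hazards named in section 19.2, and check that the consent screen on risks matches.

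The cost is a few items in existing online surveys and a protocol edit. The downsides are slightly longer surveys and more minor events to process. Unblinded self-report may still differ by arm, so the change reduces unequal capture but cannot remove it.
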